8.3. Other Efficacy Endpoints

No other efficacy endpoints are specified.

8.4. Examination of Subgroups

No subgroup analyses are planned.

9. SAFETY EVALUATION

9.1. Overview of Safety Analysis Methods

All safety summaries will be descriptive with no statistical hypothesis testing and based on the Safety Population. Safety assessments will be summarized by treatment group and overall, as specified in Section 4. All safety endpoints will be listed in by-subject data listings.

9.2. Extent of Exposure

Study drug exposure will be summarized for the CTP-543 8 mg BID and CTP-543 12 mg BID treatment groups and overall. Duration of exposure in weeks will be calculated as (date of last dose of study drug minus the date of first dose of study drug + 1 day)/7. Study drug exposure will be summarized categorically by duration of treatment in weeks ($\geq 4, \geq 8, \geq 12, \geq 16, \geq 20, \geq 24, \geq 28, \geq 36, \geq 44, \geq 52, \geq 60, \geq 68, \geq 76, \geq 84, \geq 92, \geq 100$, and ≥ 108) and will include a summary of subjects receiving ≥ 1 dose. Dose interruptions, missed doses, and partial doses will be ignored. Subjects who are lost to follow-up and were on treatment as of their last visit will be counted as receiving their last dose on the date of the last visit completed. Duration of study drug exposure in weeks as a continuous variable will also be summarized.

All summaries of exposure will be limited to exposure in CP543.5002.

Duration of cumulative study drug exposure in weeks for subjects who entered the OLE will be calculated as (OLE treatment end date – OLE treatment start date – the number of days of missed dose + 1)/7. Duration of cumulative study drug exposure will be summarized and calculated in the same manner as study drug exposure, except that any period of dose interruptions or missed doses will be subtracted. If the reason not dosed is “dose interruption”, it will be counted as a missed dose regardless of the actual number of tablets taken. If the reason not dosed is “missed dose” or “partial dose” and no tablets were taken, it will be treated as a missed dose; if the reason not dosed is “missed dose” but 1 tablet was taken, it will be treated as a partial dose.

Duration of exposure up to a qualifying dose change in CP543.5002 will be summarized as a categorical measure based on treatment sequence between the qualifying study and initial dosing in CP543.5002, as follows: Placebo to 8 mg BID, Placebo to 12 mg BID, 8 mg BID to 8 mg BID, and 12 mg BID to 12 mg BID. Duration of exposure up to a qualifying dose change for subjects previously on placebo will be separately tabulated from that of subjects previously on active drug in the qualifying study. For purposes of these tabulations, if a subject experiences a qualifying dose change, duration of exposure will be counted up to the qualifying dose change. Dose interruptions, missed doses, and partial doses will be ignored.

Duration of exposure after a qualifying dose change in the OLE study will be summarized as a categorical measure based on treatment sequence for subjects with any qualifying dose change in CP543.5002. The following treatment sequences will be used (based on treatment sequence within CP543.5002): 12 mg BID to 8 mg BID and 8 mg BID to 12 mg BID. For purposes of this tabulation, the relevant duration of exposure will be the last dose of study drug in CP543.5002 minus the date of the first qualifying dose change + 1 day. Therefore, if a subject experiences

more than one qualifying dose change, the subject will be classified according to the first qualifying dose change. Dose interruptions, missed doses, and partial doses will be ignored.

9.3. Adverse Events

An AE is any untoward medical occurrence that may appear or worsen in a subject during the course of a study. It may be a new intercurrent illness, a worsening concomitant illness, an injury, or any concomitant impairment of the subject's health, including laboratory test values, regardless of etiology. Any worsening (i.e., any clinically significant adverse change in the frequency or intensity of a pre-existing condition) should be considered an AE. A diagnosis or syndrome should be recorded on the AE page of the eCRF rather than the individual signs or symptoms of the diagnosis or syndrome. A worsening of the condition under study, alopecia areata, will not be reported as an AE.

All subjects will be monitored for AEs during the study. Assessments may include monitoring of the following parameters: the subject's clinical symptoms, laboratory, physical examination findings, or findings from other tests and/or procedures.

AEs will be coded using MedDRA version 23.1 and summarized by treatment group, system organ class, and preferred term.

An AE with a start date before the date of the first dose of study drug in CP543.5002 (i.e., generally Day 1), will be considered a pre-treatment AE. TEAEs will be defined as any AE that occurs on or after the day of administration of the first dose of study drug. Non-serious AEs are collected until completion of the study or the Early Termination Visit. Serious adverse events are reported through 30 days beyond the last dose of study drug. The number and percentage of subjects who report TEAEs will be summarized by treatment group, system organ class, and preferred term.

If a subject changes dose during the study, AEs will be considered treatment-emergent with respect to the most recent dose taken prior the start of the AE and will be tabulated under that treatment column. This may result in some subjects being included in more than one treatment column.

TEAEs will also be summarized by intensity as well as relationship to study drug.

Partial dates will be imputed for the purposes of defining TEAEs as follows:

- For a missing start day where the month and year are present, the start day will be set to the first day of the month, unless 1) the first day of the month is before the date of administration of study drug and the month and year are the same as the month and year of the date of administration of study drug, and 2) the end date is on or after the date of administration of study drug or the end date is completely missing, in which case the start day will be set to the first day of administration of study drug.
- For a missing start day and month where the year is present, the start day and month will be set to January 1st, unless 1) January 1st is before the date of administration of study drug, and 2) the end date is on or after the date of administration of study drug or the end date is completely missing, in which case the start day and month will be set to that of the first date of administration of study drug.

Sun Pharmaceutical Industries, Inc.
Statistical Analysis Plan – CP543.5002

- For a missing end day where the month and year are present, the end day will be set to the last day of the month, unless the month and year are the same as the month and year of the last visit date for the subject, in which case the end day will be set to that of the subject's last visit date.
- For a missing end day and month where the year is present, the end day and month will be set to the subject's last visit date, unless the year of the subject's last visit date is greater than the end year, in which case the end day and month will be set to December 31st.

For an entirely missing start date, the adverse event will be deemed treatment emergent unless the end date is before the first date of administration or, in the case of a partial end date, it is clear from the available date parts that the end date is prior to the date of administration.

Subjects who report the same preferred term on multiple occasions will be counted once for the preferred term: under the highest severity when summarized by severity and under the closest relationship to study drug when summarized by relationship. Missing severity or relationship will not be imputed. If a subject reports multiple preferred terms for a system organ class, the subject will be counted only once for that system organ class.

An overall TEAE summary table by treatment group and overall with the total number of TEAEs and the number and percentage of subjects with at least one of the following will be presented: TEAE, serious TEAE, serious related TEAE, TEAE leading to study drug interruption, TEAE leading to dose reduction, TEAE leading to study discontinuation, TEAE leading to death, mild TEAE (CTCAE grade 1), moderate TEAE (CTCAE grade 2), severe TEAE (CTCAE grade 3 or above), mild related TEAE (CTCAE grade 1), moderate related TEAE (CTCAE grade 2), severe related TEAE (CTCAE grade 3 or above), related TEAE, possibly related TEAE, probably related TEAE, definitely related TEAE, not related TEAE, unlikely related TEAE, related serious TEAE, possibly related serious TEAE, probably related serious TEAE, definitely related serious TEAE, not related serious TEAE, unlikely related serious TEAE. “Related” TEAEs will be defined as TEAEs which the study investigator has categorized as possibly, probably, or definitely related to study drug. “Not related” TEAEs will be defined as TEAEs which the study investigator has categorized as unlikely or not related to study drug. “Related” serious TEAEs and “not related” serious TEAEs will be defined analogously for serious TEAEs. For each severity category, the subject will be counted once at the subject’s maximum level of severity. For each relatedness category, subjects will be counted once at the subject's maximum level of relatedness.

The number and percentage of subjects who experience TEAEs and the total number of TEAEs will be summarized by treatment group and overall for the following:

- By system organ class and preferred term
- By severity/intensity (mild [CTCAE grade 1], moderate [CTCAE grade 2], or severe [CTCAE grade 3 or above]), system organ class, and preferred term
- By maximum severity/intensity (mild [CTCAE grade 1], moderate [CTCAE grade 2], or severe [CTCAE grade 3 or above]), system organ class, and preferred term
- By relationship to study drug, system organ class, and preferred term

Sun Pharmaceutical Industries, Inc.
Statistical Analysis Plan – CP543.5002

- By maximum relationship to study drug, system organ class, and preferred term
- Serious TEAEs by system organ class and preferred term
- Serious TEAEs by relationship to study drug, system organ class, and preferred term
- Serious TEAEs by maximum relationship to study drug, system organ class, and preferred term
- TEAEs resulting in study discontinuation by system organ class and preferred term
- TEAEs that result in study drug dose interruption by system organ class and preferred term
- TEAEs that result in study drug dose reduction by system organ class and preferred term

By-subject listings will include all AEs. TEAEs will be flagged.

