## 10. ADVERSE EVENTS

### 10.1. Definition of Adverse Event

An adverse event is any untoward medical occurrence that may appear or worsen in a patient during the course of a study. It may be a new intercurrent illness, a worsening concomitant illness, an injury, or any concomitant impairment of the patient's health, including laboratory test values, regardless of etiology. Any worsening (i.e., any clinically significant adverse change in the frequency or intensity of a pre-existing condition) should be considered an adverse event. A diagnosis or syndrome should be recorded on the adverse event page of the eCRF rather than the individual signs or symptoms of the diagnosis or syndrome. A worsening of the condition under study, alopecia areata, will not be reported as an adverse event.

All patients will be monitored for adverse events during the study. Assessments may include monitoring of the following parameters: the patient's clinical symptoms, laboratory, physical examination findings, or findings from other tests and/or procedures.

An adverse event reported after informed consent, but before the first dose of study drug (i.e., Day 1), will be considered a pretreatment adverse event and will be captured on the eCRF. Adverse events will be considered treatment-emergent if the onset is after the first dose of study drug or if an ongoing Adverse Event worsens after dosing is initiated.

An abnormal laboratory value is considered to be an adverse event if the abnormality:

- results in discontinuation from the study;
- is judged by the Investigator to be of significant clinical importance requiring treatment, modification/interruption of investigational product dose, or any other therapeutic intervention

Regardless of severity grade, only laboratory abnormalities that fulfill a seriousness criterion need to be documented as a serious adverse event.

If a laboratory abnormality is one component of a diagnosis or syndrome, then only the diagnosis or syndrome should be recorded on the adverse event eCRF. If the abnormality was not a part of a diagnosis or syndrome, then the laboratory abnormality should be recorded as the adverse event. If possible, the laboratory abnormality should be recorded as a medical term and not simply as an abnormal laboratory result (e.g., record thrombocytopenia rather than decreased platelets).

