#### **11.2.3.1. Adverse Events**

Treatment-emergent adverse events (TEAEs) will be defined as any adverse event that occurs after administration of the first dose of study drug until completion of the study or the Early Termination Visit. The number and percentage of patients who report TEAEs will be summarized by system organ class and preferred term.

Treatment emergent adverse events will also be summarized by intensity as well as relationship to study drug.

Patients who report the same preferred term on multiple occasions will be counted once for the preferred term: under the highest severity when summarized by severity and under the closest relationship to study drug when summarized by relationship. If a patient reports multiple preferred terms for a system organ class, the patient will be counted only once for that system organ class.

The number and percentage of patients who experience TEAEs will be summarized by dosing regimen for the following:

- By system organ class and preferred term
- By severity/intensity, system organ class, and preferred term
- By relationship to study drug, system organ class, and preferred term
- Serious adverse events by system organ class and preferred term
- Serious adverse events by relationship to study drug, system organ class, and preferred term

- Adverse events resulting in discontinuation of study drug by system organ class and preferred term
- Adverse events that result in study drug dose interruption by system organ class and preferred term

By-patient listings will be provided for any deaths, serious adverse events, and adverse events leading to discontinuation of treatment.

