2. PURPOSE OF THE ANALYSES

This statistical analysis plan (SAP) provides a detailed description of the strategy and statistical methodology to be used for analysis of data from the CP543.5002 current protocol version.

The purpose of the SAP is to describe the pre-specified statistical approaches to the analysis of study data prior to database lock. This analysis plan is meant to supplement the study protocol. If differences occur between analyses described in the SAP and the current protocol, those found in this SAP will assume primacy. Any deviations from this plan will be described in the Clinical Study Report (CSR).

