6.4. Medical History

Medical history and AE data from CP543.3001 and CP543.3002 may be recorded on the medical history eCRF CP543.5002. Newly discovered medical history and worsening AEs prior to first dose will also be collected in the eCRF for CP543.5002. Medical history will be coded with the MedDRA terminology Version 23.1 and summarized as counts and percentages for the Safety Population by treatment group and overall, system organ class, and preferred term. A subject will be counted only once for each condition. Conditions will be presented in by-subject listings, including the verbatim investigator description of the relevant medical condition, the coded terms (system organ class, preferred term), start date, end date, and whether or not the condition is ongoing.

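### Three definitions of a treatment-emergent AE disagree: only Protocol 10.1 counts an ongoing event that worsens after dosing, and the governing SAP rule can leave such an event out of the TEAE tables

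*SAP*

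**What the plan says.** Three places define a treatment-emergent AE (TEAE).

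- Protocol Section 10.1 has two limbs. An AE qualifies "if the onset is after the first dose of study drug or if an ongoing Adverse Event worsens after dosing is initiated".
- Protocol Section 11.2.3.1, in the statistics chapter, has one limb: "any adverse event that occurs after administration of the first dose of study drug until completion of the study or the Early Termination Visit".
- SAP Section 9.3 also has one limb: "TEAEs will be defined as any AE that occurs on or after the day of administration of the first dose of study drug". It adds the converse, that "An AE with a start date before the date of the first dose of study drug in CP543.5002" is a pre-treatment AE.

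Where the SAP and the protocol differ, SAP Section 2 says that "those found in this SAP will assume primacy". SAP Section 12 lists one change from the protocol, a laboratory summary; the TEAE definition is not mentioned.

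On recording, SAP Section 6.4 says: "Medical history and AE data from CP543.3001 and CP543.3002 may be recorded on the medical history eCRF CP543.5002". It adds that AEs worsening before the first dose are collected in this study's eCRF, and it has no matching sentence for worsening after the first dose. Protocol Section 10.5 asks for one entry per AE, and Section 10.2.4 for start and stop dates. Neither says whether a worsening opens a new entry.

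**The concern.** Long-term safety is a stated objective. The Baseline visit falls on the last day of a 24-week parent trial, so some patients can be expected to enter with an AE still ongoing. Patients who had placebo in the parent trial start active drug at that point. If one of their ongoing events worsens, that is first-exposure safety information.

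Under a rule that reads only the start date, such an event can be classed as pre-treatment however far its grade rises on drug. It would then be missing from the TEAE incidence table and from the tables by severity, relationship, seriousness, dose interruption, dose reduction and study discontinuation, all of which SAP 9.3 builds on TEAEs. Any error would be towards undercounting, and what goes uncounted would be the raised grade.

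**Working it through.** There is no figure in the plan to reproduce: the study is descriptive and the documents give no AE counts. The check is to take an AE that is ongoing at the first CP543.5002 dose and worsens afterwards, and apply each definition to it.

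| How the worsening is recorded | Protocol 10.1 | Protocol 11.2.3.1 | SAP 9.3 |
|---|---|---|---|
| (a) Original event held as medical history; worsening entered as a new AE dated after first dose | TEAE | TEAE | TEAE |
| (b) One AE record, original start date kept, grade raised | TEAE | Unclear | Pre-treatment |
| (c) One AE record, start date entirely missing, end date not before first dose | TEAE | Unclear | TEAE by the missing-date rule |

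**Where the loss arises.** Only row (b) gives a loss. There the event drops out of every TEAE table in SAP 9.3. It stays in the by-subject AE listing, without a TEAE flag.

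**Does the general AE definition close the gap?** SAP 9.3 says that any clinically significant worsening of a pre-existing condition is itself an AE. Read with the TEAE sentence, this supports row (a). It does not settle row (b), because the pre-treatment test looks only at the start date on the record. Protocol 10.1 contains the same statement about worsening and still adds an explicit worsening limb, so the protocol did not treat the statement as enough.

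**Comparison with the rest of the SAP.** For laboratory parameters graded independently of baseline, SAP 9.5 compares the baseline value with the post-baseline value. For ECG, SAP 9.6.3.1 requires a criterion to be met after dosing and not at baseline, and counts a missing baseline as treatment-emergent. In SAP 9.3 an AE with no start date at all is treatment-emergent unless it ended before dosing. An AE with a known earlier start and a known worsening on drug therefore gets the least inclusive treatment.

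**Size.** The loss is zero if every worsening is entered as a new dated AE. Otherwise it equals the number of row (b) events. The documents give neither the number of AEs ongoing at Day 1 nor the recording practice. Any percentage would have to assume the very practice that is in doubt, so none is offered.

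**The case against.** The strongest case on the other side is that the path to a loss is narrow.

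- SAP 9.3 treats a worsening as an AE in its own right, and SAP 6.4 allows parent-trial AEs to be carried as medical history. Where both are followed, the worsening is a new AE and is counted.
- AEs in this study are recorded from consent. Consent is taken at the Baseline visit, when drug is also dispensed, and an AE starting on the day of first dose counts as a TEAE. Few AE-page records should therefore start before the first dose.
- Recording conventions may be set out in the Site Operations Manual or the Data Management Plan, which the protocol mentions but which are not available here.
- Affected events remain in the listings. SAP 9.4 lists deaths, serious AEs and AEs leading to discontinuation without restricting them to TEAEs. Laboratory and blood-pressure worsening is also summarised separately, in SAP 9.5 and 9.6.1.

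All of this stands as a limit on the likely consequence. It does not reconcile the definitions. The medical-history route is permissive, and silence on recording does not show that new records are opened any more than it shows that old ones are overwritten.

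A reader might infer that the SAP alone abandoned the protocol's rule without declaring it. The documents do not support that. Protocol 11.2.3.1, the planned-analysis section, also lacks the worsening limb, and on that point the SAP follows it.

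**Conclusion.** The point holds as a conflict of definitions with a conditional consequence. Protocol 10.1 counts an ongoing AE that worsens after dosing. Protocol 11.2.3.1 does not say so. SAP 9.3, which governs, classes any AE with a start date before the first CP543.5002 dose as pre-treatment. An event kept on its original record with a raised grade is therefore a TEAE under Protocol 10.1 and absent from the TEAE tables.

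A reader might go further and conclude that worsened carry-over events disappear from the safety reporting, or that TEAE incidence is biased downwards by an estimable amount. Neither is established. The events stay listed, the loss depends on a recording practice that neither document states, and its size cannot be computed. The point is still worth correcting before database lock, because the rule as written conflicts with the protocol and the correction is cheap.

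**What to change.** In SAP 9.3, restore the Protocol 10.1 limb: an AE that started before the first CP543.5002 dose and increases in CTCAE grade on or after that dose is a TEAE.

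Implement it by a single route for each event, so that nothing is counted twice in the total number of TEAEs:

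- a new AE record dated at the worsening; or
- a flag on the existing record, only where no new record exists.

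The new record is the cleaner route. The AE fields named in Protocol 10.5 do not include a date of grade change. SAP 9.3 assigns an AE to the dose column of the most recent dose before its start, so a flagged event also needs the date of worsening to be placed correctly.

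Align Protocol 11.2.3.1 with 10.1. If the protocol is not amended again, state the chosen definition in SAP Section 12.

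The cost is one sentence in the SAP, a small derivation and a note to sites. TEAE counts may rise slightly.

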### **8.1.1. Management of Risk with Janus Kinase (JAK) Inhibitors**

On 23 January 2023, EMA's human medicines committee (CHMP) endorsed the measures recommended by the Pharmacovigilance Risk Assessment Committee (PRAC) to minimize the risk of serious side effects with approved Janus kinase (JAK) inhibitors used to treat several chronic inflammatory disorders. These recommendations were based on a review of available data, including the final results from a clinical trial of the JAK inhibitor Xeljanz (tofacitinib) and preliminary findings from an observational study involving Olumiant. These side effects include cardiovascular conditions, blood clots, cancer and serious infections. Janus kinase (JAK) inhibitors used to treat chronic inflammatory disorders are linked to a higher risk of major adverse cardiovascular events (MACE), venous thromboembolism (VTE), malignancy, serious infections and all-cause mortality.

As CTP-543 is an investigational product in the JAK inhibitor class of drugs, CTP-543 should be used with caution in patients with risk factors for blood clots in the lungs and in deep veins (venous thromboembolism, VTE), patients at increased risk of major cardiovascular problems (such as heart attack or stroke), those who smoke or have done so for a long time in the past and those at increased risk of cancer. Any patients presenting with an increased risk should be withdrawn per Section 7.3.

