Following reports of thrombosis with 12 mg BID after long-term administration of CTP-543 and discussions with the US Food and Drug Administration (FDA), the 12 mg BID dose was immediately discontinued and communicated under an Urgent Safety Measure. Due to implementation of this urgent safety measure, all patients previously assigned to the 12 mg BID dose will be dose reduced to the 8 mg BID dose, should they elect to continue in the trial, for the duration of the trial up to a total of 52 weeks for non-responders or a maximum of 108 weeks for responders.

At the Week 52 visit, subjects will be assessed for treatment success (Responders) defined as subjects having an absolute SALT score of ≤ 20 . These Responders will continue in the OLE extension for an additional 52 weeks. Non-responders will complete the study at Week 52. Additionally, subjects should be withdrawn from the study if in the Investigator's opinion

Sun Pharmaceutical Industries, Inc.
Statistical Analysis Plan – CP543.5002

continued study participation is undesirable or the risk-benefit profile has become unfavorable. Additional withdrawal criteria can be found in Section 7.3 of the protocol.

Subject safety will be monitored throughout the study. During the first 12 weeks, hematology, serum chemistry, and lipids will be conducted under fasted conditions every 4 weeks. Following 12 weeks on treatment, subjects will return to the clinic every 8 weeks for safety assessments until the completion of the study or until withdrawal from the study. At each study visit, an assessment should also be undertaken for any changes in the physical exam, or symptoms such as pain, swelling or tenderness in leg(s), persistent breathing difficulties or shortness of breath, or severe headache, that are suggestive of an increased risk of thromboembolism. Patients must be withdrawn if they have a prior history of thrombotic event(s) or experience a thromboembolic event.

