9.4. Deaths, Serious Adverse Events, and Other Significant Adverse Events

A serious adverse event is an AE that fulfills the following criteria:

- Is fatal (results in death);
- Is life-threatening (Note: the term "life-threatening" refers to an event in which the subject was at risk of death at the time of the event; it does not refer to an event that could hypothetically have caused death had it been more severe);
- Requires inpatient hospitalization or prolongation of existing hospitalization (hospitalization is defined as an inpatient admission, regardless of length of stay);
- Results in persistent or significant disability/incapacity (a substantial disruption of the subject's ability to conduct normal life functions);
- Is a congenital anomaly/birth defect; or
- Constitutes an important medical event that may jeopardize the subject or may require medical or surgical intervention to prevent one of the other outcomes listed above.

Serious adverse events will be summarized according to Section 9.3.

By-subject listings will be provided for any deaths, serious adverse events, and AEs leading to discontinuation of treatment. TEAEs that result in dose interruption or reduction will also be identified.

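### The SAP pre-specifies no grouped thromboembolic or MACE category, so the number of patients with any such event by dose must be assembled post hoc from separate terms and listings

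*SAP*

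**What the plan says.** SAP 3 gives the reason for the mid-study dose change: "Following reports of thrombosis with 12 mg BID after long-term administration of CTP-543", followed by discussions with the regulator, led to 12 mg BID being discontinued under an urgent safety measure. Protocol 8.1.1 adds that JAK inhibitors used for chronic inflammatory disorders "are linked to a higher risk of major adverse cardiovascular events (MACE), venous thromboembolism (VTE), malignancy, serious infections and all-cause mortality".

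The adverse event analysis is in SAP 9.3: "The number and percentage of subjects who report TEAEs will be summarized by treatment group, system organ class, and preferred term". The counting rules are "Subjects who report the same preferred term on multiple occasions will be counted once for the preferred term" and "If a subject reports multiple preferred terms for a system organ class, the subject will be counted only once for that system organ class". Events are assigned to the most recent dose taken before onset, so a patient who changes dose can appear in more than one column.

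Section 9.3 goes beyond plain term tables. It plans summaries by severity and relationship, separate tables for serious events and for events leading to discontinuation, interruption or dose reduction, and an overall summary with rows that include "TEAE leading to study drug interruption, TEAE leading to dose reduction, TEAE leading to study discontinuation, TEAE leading to death". All adverse events are listed by subject.

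SAP 9.4 covers deaths, serious events and other significant events. It states "Serious adverse events will be summarized according to Section 9.3" and adds listings of deaths, serious events and events leading to discontinuation. It defines no event group by medical concept. In the SAP text supplied, thrombosis and thromboembolism appear only in the protocol summary. Protocol 11.2.3.1 has no grouping either.

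**The concern.** A clot can be coded under more than one preferred term; Protocol 8.1.1 itself distinguishes clots in the lungs from clots in deep veins. A table with one row per term therefore does not directly answer how many patients on each dose had any thromboembolic event. The same holds for MACE, which combines different diagnoses by construction.

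The SAP leaves that total to be built afterwards. Whoever builds it decides which terms count while seeing which terms occurred. With few events, including or excluding one term can move the result noticeably.

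The SAP shows that this kind of pre-specification was within reach. Section 9.5 defines composite liver criteria, potential Hy's law counts and eDISH plots in advance. Section 8.2.3.1 was written for patients reduced from 12 mg to 8 mg on or after 28 Apr 2023. The event that caused the reduction has no counterpart in the safety section.

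**Working it through.** The documents give no event count, rate or sample size for this point, so there is no stated figure to reproduce. The check has three parts.

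**1. Which planned outputs could give the total?**

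| Planned output (SAP) | What it gives for thromboembolism or MACE |
|---|---|
| Organ class and term tables (9.3) | Patients per single term, by dose at onset |
| Severity, relationship and serious tables (9.3) | The same terms, subdivided |
| Discontinuation table (9.3) | Withdrawn cases, again by organ class and term |
| Overall summary (9.3) | Any, serious, fatal and similar rows; no row for either event group |
| Listings (9.3, 9.4) | Every case, with no rule for which terms belong |

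None gives patients with at least one event across a defined set of terms.

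**2. What do the term rows determine?** Let c₁, …, c_k be the patient counts in k relevant term rows of one column. Each patient counts once per row but may appear in several rows, so

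max(c) ≤ distinct patients ≤ sum(c).

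With assumed counts:
- rows of 2 and 2: from 2 to 2 + 2 = 4 patients
- rows of 3, 2 and 1: from 3 to 3 + 2 + 1 = 6 patients
- rows of 2, 1, 1 and 1: from 2 to 2 + 1 + 1 + 1 = 5 patients

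The organ-class row does not close the gap, because it also counts unrelated terms and does not remove duplicates across classes.

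**3. What form should the total take?** A simple percentage by dose fits badly. Continuing 12 mg patients move to 8 mg, so columns overlap. Treatment also lasts up to 52 weeks for non-responders and up to 108 weeks for responders, a ratio of 108/52 = 2.1. A person-time rate handles both:

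rate = 100 × D / PY,

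where D is patients with a first event at that dose and PY is patient-years at that dose up to the first event. The exact Poisson 95% limits are 100 × χ²(0.025; 2D)/(2 PY) and 100 × χ²(0.975; 2D + 2)/(2 PY).

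Illustration with assumed D = 3, where the limits on the count are 0.619 and 8.767:
- PY = 150: 300/150 = 2.0 per 100 patient-years; limits 61.9/150 = 0.4 and 876.7/150 = 5.8
- PY = 200: 300/200 = 1.5; limits 61.9/200 = 0.3 and 876.7/200 = 4.4

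The interval would be wide. It shows how little a small count can establish.

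**The case against.** The strongest reply is that nothing is lost. Counts per term by dose at onset are planned, and every event is listed. Protocol 7.3 requires withdrawal after a thromboembolic event, so on-study cases should reach the discontinuation table and listing. Withdrawal also makes a second clot under another term unlikely, which leaves mainly simultaneous diagnoses in one patient to widen the bounds above. All of this stands, and it limits the point to pre-specification. It does not supply a term list, and MACE has no named withdrawal rule of its own.

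A reader might infer that events are tabulated only by organ class and term, or that the report would hold no patient count of thrombosis. The documents do not support either reading, given the tables set out above. Nor do they support extending the point to deaths or serious infections: fatal events have their own summary row, and serious events are already tabulated by organ class. If no relevant term occurs, the planned tables already show that.

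A reader might also see a collection gap, since "Non-serious AEs are collected until completion of the study or the Early Termination Visit" while serious events are reported for 30 days after the last dose. That is a separate and narrow matter. It needs a clot judged non-serious that starts after the final visit, and the seriousness definition includes important medical events that may require intervention.

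Three further replies carry less weight:
- **The study is descriptive.** A grouped rate is descriptive too, and the Protocol synopsis allows confidence intervals as exploratory.
- **The integrated safety analysis may cover it.** That plan was not available, and the data freeze described in SAP 8.1.2 is late 2022, before the dose reductions of April 2023.
- **The table shells may include it.** This is possible. SAP 4.1 says they are attachments, and they were not available.

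**Conclusion.** The point holds in a limited form. SAP 9.3 and 9.4 define no thromboembolic or MACE group, so the number of patients with any such event by dose has to be put together after the data are seen. Under SAP 8.1.2 that analysis would be reported as post hoc. This is a weak position for the event that changed the trial.

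The effect cannot be sized from the documents. In the assumed examples the planned term tables leave the patient count uncertain by up to a factor of 2.5 (2 to 5). Mandatory withdrawal should make the real uncertainty for clots smaller, and the listings can remove it once the terms are chosen. What the listings cannot restore is a term choice made independently of the results.

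The conclusion rests on the SAP text alone and would fall if the unseen shells already contain a grouped table with a fixed term list. It is a cheap improvement and not a flaw that invalidates the safety analysis.

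**What to change.** In SAP 9.4, add one table and one listing for two groups: (a) any venous or arterial thromboembolic event and (b) MACE. Define each by a MedDRA term list fixed before database lock and attached to the SAP.

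Report, by dose at onset and overall:
- patients with at least one event
- the rate per 100 patient-years, with an exact 95% interval labelled descriptive
- time from first active dose, using the first-active-dose date already needed for the pre-zero baseline in SAP 6.2

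Split exposure at the actual dose change, using the dosing dates behind SAP 9.2. This matters because SAP 4.1 assigns events to the most recent dose but splits exposure only at a qualifying dose change. Numerator and denominator should follow one rule. State in a footnote whether events after the last dose are included.

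No new visits, data collection or separate death and serious-infection groups are needed. The cost is a term list, a small amount of programming, and a visible pooled rate with a wide interval.
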